4.2.3 Control – SDC group

SDC (Arm2) participants will be informed they have periodontitis and asked to continue their usual dental treatment, incurring the standard costs for their treatment. If they have a dentist the participant will already know they have gum disease and will be having treatment for it with the associated costs, they will not incur any additional costs due to study participation. If participants do not have a dentist they may choose to continue to abstain from dental treatment, in which case there will be no additional costs. If participants do not have a dentist but decide to see a dentist, their treatment costs will be no different to those normally incurred by patients.

Arm2 (SDC) participants who attend a dentist will be provided with periodontal treatment as part of usual dental care, however a recent NHS-GDP-practice survey showed active gum disease in 52.9% of patients even though 83.6% reported dental attendance in the previous year [70]. Without tailored personalised oral hygiene instruction, gum bleeding reduction is unlikely to be achieved [26,69].

With ethical consideration and PPI feedback, those in Arm2 will be offered free IDC after their 12months on the trial. For those who can complete an 18-month cognitive assessment within the study timeframe, the IDC will be offered after this has taken place.

In addition, at the end of the study we will contact participants' regular dentists to share the IDC treatment regime performed and support its uptake in practice.

4.2.4 Visits at 6, 12 and 18 months

All participants will be invited to return to the Brain Centre, Southmead Hospital at 6 and 12 months for cognitive and periodontal assessments and to donate samples of blood and saliva. For those participants who remain in the study to 18 months, the 18-month assessment will be cognitive only and conducted over video if possible, with face-to-face assessment used if participants are unable to use a video link.

4.3 Assessments

Baseline, 6 and 12 months:

- Cognitive assessment: Clinical Dementia Rating Sum of Boxes (CDR-SB): an appropriate and widely used primary outcome measures for early and late dementia [71]. Alzheimer's Disease Assessment Scale Cognitive subscale (ADAS-Cog11) [72], and Bristol Activities of Daily Living Scale (BADLS), measuring functional ability [73].
- Periodontal assessment: Bleeding on Probing (BOP) (yes/no); periodontal pocket depths (mm)four gingival sites/tooth; dental plaque- O'Leary plaque index (yes/no)-four surfaces/tooth [74].
- Blood/saliva (laboratory research): Assessed for inflammatory response and bacterial load to confirm that bacteraemia and that pathogens have been reduced by the treatment.

18-months (cognitive only):

 Cognitive assessment: ADAS-Cog assessment over video. This assessment has been adapted and used successfully by the team in a recent previous study during the covid-19 pandemic. There is a precedent for comparing video and face-to-face ADAS-Cog, although this is not yet validated or mainstream. This assessment will not be audio-recorded, the assessor will record scores in the same way as they would in a face-to-face scenario.

Both the study dentist and cognitive assessor will be blinded to the treatment received by the participant.

Qualitative assessments (measuring impact on participants/dentists)

These assessments will be undertaken by the central research team at 12-month visit(participants), or on-line via Zoom/similar once the treatment course(s) is/are complete for their participants (dentists who delivered IDC):

In-depth, semi-structured, qualitative interviews will be carried out with 10-12 participants (5-6 from the control and 5-6 from the intervention group) as well as up to 8 of the dental teams who delivered the intervention. Interviews will follow a topic guide that will assess participants' acceptability of the intervention, barriers and facilitators to participation, the ingredients of the intervention that they felt had positively or negatively impacted on their behaviour and overall perceptions about the feasibility of the study. Dental teams will be asked similar questions, in addition to questions aimed to assess treatment fidelity with regard to the motivational intervention. Interviews will be audio-recorded and fully transcribed. It is expected that these will take about 30 minutes for each patient participant and 15 minutes for each dental practitioner.

Data will be thematically analysed using an inductive approach and following Braun and Clarke's (2006) [75] 6-stage process.

4.4 Statistics and Data Analysis

At randomisation participants will be stratified according to whether they have MCI or early AD as follows: Cognition stratification will be based on the Clinical Dementia Rating Sum of Boxes (CDR-SB): score with scores above 0.5 classed as early AD [71]. In the full trial the randomisation will also be stratified by periodontal disease classed as mild for periodontal pockets >4mm and <6 mm with bleeding on probing and severe: one or more periodontal pocket(s) \geq 6 mm [67].

After data lock a CONSORT-diagram will be produced showing recruitment/consent/follow-up rates and treatment compliance with reasons for loss to follow-up. Progression rates for MCI/AD will

include all participants. The 80% confidence interval for all effect sizes (laboratory data/periodontitis scores/MCI or AD progression) will be calculated to assist with planning the full trial, illustrating proof of concept for sensitivity to change, ensuring effect sizes used in planning the definitive trial are plausible.

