4.2 Study visits

4.2.1 Screening (post informed consent) and baseline assessment

Participants who have consented to take part in the study will first be assessed for eligibility against cognitive inclusion/exclusion criteria (in addition to the already assessed capacity to consent). The study dentist will then assess eligible volunteers for dental inclusion/exclusions. Participants meeting all inclusion criteria and none of the exclusion criteria will be enrolled. Baseline scores of cognitive and periodontal status will then be completed and samples of blood and saliva taken for inflammatory markers. All participants will receive oral and written oral hygiene education, toothpaste, a power toothbrush and an appointment to return to the Brain Centre after 6-months.

Immediately post the screening appointment, once baseline cognitive and periodontal status results can be combined, a Stratified Randomisation Schedule (computer-generated, concealed from recruiter until consent obtained) will be used to randomise participants to IDC(Arm1) or SDC(Arm2) stratified by cognitive status (MCI or early AD) and periodontal status (mild or severe). Participants will be contacted by their preferred method to confirm their randomisation to Arm1/Arm2.

As participants who do not meet screening criteria may be disappointed, they will be advised about other opportunities to become involved in research, such as participation in Patient Advisory Groups, or other studies that they may be eligible to take part in.

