6. RECRUITMENT

6.1 Eligibility criteria

6.1.1 Inclusion Criteria:

- Adults with amnesic or multidomain MCI [76] or early-stage AD [77] diagnosed using standard diagnostic criteria [76-78]. Participants are expected to have an Addenbrooke's, Montreal Cognitive Assessment (MoCA) or equivalent cognitive score in the typical range for early-AD/MCI (60- 94yrs)[79-80]. For Addenbrook's the typical range is 65-92 and for MoCA, 16-28. However, if participants clinically diagnosed with AD, meet test requirements, retain capacity and perform better or worse on Addenbrooke's Cognitive Examination (ACE-III) than expected, trial inclusion may proceed (case-by-case basis) as assessed by [name]/another team dementia expert. This will make the trial as inclusive as possible and not exclude people with, e.g. prominent visual disturbance that disproportionately affects cognitive test performance such that scores do not reflect true cognitive ability or those with particularly high baseline function.
- People who retain capacity to consent: Determined by a fully trained assessor. Where there is doubt about capacity, we will utilise a formal decision-making tool built around UK-legislation (MacCAT-T Brief screening tool [81]) and the decision taken by [name]/another team dementia expert—in line with guidance [82].
- 3. A project partner (e.g. carer/friend) to attend at least the first appointment with participant (In our pilot study we amended the protocol to allow participants to attend thereafter without their partner as requested by some volunteers).
- 4. >6 teeth for adequate assessment of periodontitis
- 5. Aged 60yrs+
- 6. Periodontal pockets >4mm with Bleeding on Probing (BOP).

6.1.2 Exclusion criteria:

- 1. Uncontrolled diabetes
- 2. Uncontrolled dental disease other than periodontitis
- 3. Scores ≥3 on the American Society of Anaesthesiologists Physical-Status-Classification-System.

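### The cognitive stratum calls any CDR-SB above 0.5 early AD, while eligibility separates MCI from early AD by clinical diagnosis, so the stratum may not balance diagnosis between arms

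*Protocol*

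**What the plan says.** Section 4.4 states the purpose of the factor: "At randomisation participants will be stratified according to whether they have MCI or early AD as follows". The rule that follows is: "Cognition stratification will be based on the Clinical Dementia Rating Sum of Boxes (CDR-SB): score with scores above 0.5 classed as early AD". By implication a total of 0 or 0.5 is filed as MCI. Reference 71 is attached to the rule, but no derivation is given.

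Section 4.2.1 describes randomisation as "stratified by cognitive status (MCI or early AD) and periodontal status (mild or severe") and does not say how cognitive status is determined.

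Section 6.1.1 admits "Adults with amnesic or multidomain MCI [76] or early-stage AD [77] diagnosed using standard diagnostic criteria [76-78"]. It gives expected screening ranges for the two conditions together, "For Addenbrook's the typical range is 65-92 and for MoCA, 16-28", and no CDR-SB range for either. Nowhere does the protocol say how to file a participant whose diagnosis is MCI and whose CDR-SB exceeds 0.5.

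On analysis, section 4.4 says that progression rates will "include all participants. The 80% confidence interval for all effect sizes (laboratory data/periodontitis scores/MCI or AD progression) will be calculated". It specifies no report by cognitive stratum.

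**The concern.** Two rules in one protocol decide who counts as MCI and who as early AD: a diagnosis at entry and a score at randomisation. They can disagree for the same person. The score threshold also appears to sit at the very bottom of a summed scale, where minimal difficulty in more than one area is enough to cross it. Disagreement would then fall mainly on people diagnosed with MCI, who would be randomised under the early AD label.

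A stratification factor is there to keep a prognostic characteristic balanced between arms. If many MCI participants join the early AD stratum, the factor balances something other than the diagnosis it is named after. The rule acts at randomisation, so a later analysis plan can adjust for the result but cannot undo the allocation. Section 4.4 also says that the full trial will stratify by periodontal disease in addition, which implies that the cognitive rule would be carried forward.

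**Working it through.** **What can be reproduced.** The 0.5 cut has no derivation in the protocol, so there is no figure on this point to reproduce. The precision statement in section 6.2 does reproduce: the exact (Clopper–Pearson) 80% interval for 40/50 is 70.9% to 87.2%, against the stated 71% to 87%. It does not depend on the cut.

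**Inputs from the protocol.** The cut is above 0.5 (section 4.4). The sample is 50, with 25 per group (section 6.2). MCI and early AD are defined by diagnosis (section 6.1.1).

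**Assumptions not in the protocol.** Six boxes, each scored 0, 0.5, 1, 2 or 3 and summed; the distribution of box scores in MCI; the number of MCI participants; the block size.

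**Step 1: where the cut sits.** Under the assumed scoring there are 5^6 = 15,625 possible box profiles. Those totalling 0.5 or less are the all-zero profile plus six with a single box at 0.5, so 1 + 6 = 7. Two boxes at 0.5 (total 1.0), or one box at 1, are classed as early AD. These are counts of profiles, not probabilities of patients.

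**Step 2: share of MCI filed as early AD.** Suppose the memory box is 0.5 and each of the other five is non-zero independently with probability q. The total stays at 0.5 only if all five are zero, so the share misfiled is 1 − (1 − q)^5.

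| q | (1 − q)^5 | share filed as early AD |
|---|---|---|
| 0.05 | 0.774 | 23% |
| 0.10 | 0.590 | 41% |
| 0.20 | 0.328 | 67% |
| 0.30 | 0.168 | 83% |
| 0.50 | 0.031 | 97% |

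Half are misfiled at q = 1 − 0.5^(1/5) ≈ 0.13, and 90% at q = 1 − 0.1^(1/5) ≈ 0.37. Nothing in the protocol points to a value of q.

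**Step 3: effect on balance.** Allocation of 50 participants was simulated 4,000 times per scenario, in permuted blocks of 4 within the cognitive strata only. The measure is the absolute difference between arms in the number of diagnosed MCI participants.

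| MCI participants misfiled | 15 MCI: mean imbalance | 15 MCI: 6 or more | 25 MCI: mean imbalance | 25 MCI: 6 or more |
|---|---|---|---|---|
| none | 1.0 | 0% | 1.0 | 0% |
| half | 2.2 | 2% | 2.5 | 5% |
| 80% | 2.6 | 5% | 2.8 | 8% |
| all | 2.7 | 7% | 2.9 | 9% |

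The first row is the minimum possible, because 15 and 25 are odd. The last row agrees with a rough check. If 25 of 50 are drawn at random into one arm, the variance of its MCI count is 25 × p(1 − p) × 25/49, where p is the MCI share. For p = 0.5 this is 3.19, so the between-arm difference has SD 2 × √3.19 = 3.57 and mean absolute value of about 0.8 × 3.57 = 2.9. For p = 0.3 it is 2.68, giving SD 3.27 and about 2.6.

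**The case against.** Several stronger readings are tempting, and the other side is right to resist them.

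- **That most MCI participants, or nearly all with multidomain MCI, will be misfiled.** The protocol gives no CDR-SB scoring, no score distribution and no MCI:AD mix. Most requires q above about 0.13 and nearly all about 0.37 or more; at q = 0.10 the share is 41%. To say that multidomain MCI is always misfiled assumes two non-zero boxes and then concludes that the total exceeds 0.5. The protocol does not equate the cognitive domains in that diagnosis with CDR boxes.
- **That the MCI stratum will be almost empty.** With 25 MCI participants, about 25 × 0.59 = 15 remain in it at q = 0.10 and about 25 × 0.33 = 8 at q = 0.20. Near-emptiness belongs to the upper end of the range.
- **That stratification fails.** Allocation is still random and the comparison of arms is not biased. The worst case costs some protection against chance imbalance.
- **That MCI/AD results will be wrong.** Section 4.4 pools all participants, section 6.2 bases the progression statement on all 50, and the entry diagnosis remains available for any description by group.
- **That the cut was borrowed from a different CDR rating.** This is conjecture. Reference 71 is cited for the cut and cannot be read here.

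The progression criteria in section 3.2 are recruitment and data completion, and the cut affects neither. These arguments limit the size of the point. They do not remove the inconsistency between sections 4.4 and 6.1.1, and they leave no rule for a diagnosed MCI participant who scores above 0.5.

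**Conclusion.** The concern holds in a limited form. Section 4.4 says it stratifies by MCI or early AD but applies a score rule that need not match the diagnosis required by section 6.1.1. If the usual six-box scoring applies, the cut is the lowest non-zero total, and some diagnosed MCI participants can be expected to be randomised as early AD. How many cannot be established from the protocol; 23% to 97% is a range over assumed values of q, with independence between boxes also assumed.

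Randomisation remains valid. The likely cost at this sample size is modest: a mean MCI imbalance between arms of at most 2.7–2.9 instead of about 1.0, and an imbalance of 6 or more in at most 7–9% of randomisations instead of none. Those upper figures require every MCI participant to be misfiled, and they rest on the assumed MCI numbers, blocks of 4 and a cognitive stratum used alone. The severity is moderate: worth correcting, but not a condition for the study to proceed.

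**What to change.** Reconcile sections 4.4 and 6.1.1. The simplest way is to state in 4.4 that the cognitive stratum is the clinical diagnosis established at entry, MCI or early AD. If a CDR-based stratum is preferred, state the scoring and keep it only with a cut shown to separate the two diagnosed groups. If any results are described by MCI/AD, use the entry diagnosis and not the stratum label.

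The cost is one sentence in the protocol and one field in the randomisation system, handled through the amendment route in section 8.3.1. No visit or assessment is added, because the diagnosis is already required for entry.

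If randomisation has begun, keep the allocations as made, tabulate entry diagnosis by stratum and arm to show how many participants were filed against their diagnosis, and adjust comparative analyses for entry diagnosis as well as the randomised stratum.

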5. STUDY SETTING

Participant appointments for screening/baseline, 6, 12 and 18 months will take place at the Bristol Brain Centre, at Southmead Hospital, North Bristol NHS Trust (NBT), and is a building operated in partnership between NBT and the University of Bristol.

Participants allocated to the IDC will be treated either at Bristol Dental Hospital (UHBW NHS Foundation Trust), or at a general dental practice that is part of the South West Dental Foundation Scheme, or the dental practice of co-Applicant [name]. Up to 10 different sites will deliver the intervention.

Qualitative work will be undertaken on-line via Zoom/Teams or similar.

Laboratory analysis of blood and saliva samples will be undertaken in University of Bristol laboratories.

6. RECRUITMENT

6.1 Eligibility criteria

6.1.1 Inclusion Criteria:

- Adults with amnesic or multidomain MCI [76] or early-stage AD [77] diagnosed using standard diagnostic criteria [76-78]. Participants are expected to have an Addenbrooke's, Montreal Cognitive Assessment (MoCA) or equivalent cognitive score in the typical range for early-AD/MCI (60- 94yrs)[79-80]. For Addenbrook's the typical range is 65-92 and for MoCA, 16-28. However, if participants clinically diagnosed with AD, meet test requirements, retain capacity and perform better or worse on Addenbrooke's Cognitive Examination (ACE-III) than expected, trial inclusion may proceed (case-by-case basis) as assessed by [name]/another team dementia expert. This will make the trial as inclusive as possible and not exclude people with, e.g. prominent visual disturbance that disproportionately affects cognitive test performance such that scores do not reflect true cognitive ability or those with particularly high baseline function.
- People who retain capacity to consent: Determined by a fully trained assessor. Where there is doubt about capacity, we will utilise a formal decision-making tool built around UK-legislation (MacCAT-T Brief screening tool [81]) and the decision taken by [name]/another team dementia expert—in line with guidance [82].
- 3. A project partner (e.g. carer/friend) to attend at least the first appointment with participant (In our pilot study we amended the protocol to allow participants to attend thereafter without their partner as requested by some volunteers).
- 4. >6 teeth for adequate assessment of periodontitis
- 5. Aged 60yrs+
- 6. Periodontal pockets >4mm with Bleeding on Probing (BOP).

6.1.2 Exclusion criteria:

- 1. Uncontrolled diabetes
- 2. Uncontrolled dental disease other than periodontitis
- 3. Scores ≥3 on the American Society of Anaesthesiologists Physical-Status-Classification-System.

6.2 Sample size

The sample size is set to 50 participants for both allowing sufficient precision around the recruitment and follow-up percentages that will appear in the consort statement, and for the parameters to show the potential proof of concept for the underlying hypothesis using the surrogate end point of blood markers of inflammation.

50 participants with 25/group will allow us precision within 10% to predict follow-up data completion rates with 80% proof of concept confidence intervals such that a data completion rate of 80% would have the 80% confidence intervals of [71%, 87%]. Effect sizes for MCI/AD progression (n=50) will have 90% power to show 80% confidence intervals do not contain zero if the effect size is larger than 0.4 standard deviations. For the 25 in the intervention arm there is 90% power to show that periodontal improvement and blood markers of inflammation have 80% confidence intervals which do not contain zero if the effect size is larger than 0.6 standard deviations.

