Dissemination: Throughout, we will keep everyone informed by means of talks, publications and social media posts. Slowing the progress of Alzheimer's by improving dental health could dramatically improve quality of life for sufferers and carers. If the study provides evidence to support a larger trial and shows the personalised dental care plan is helping, we would be able to strongly recommend the use of a personalised dental plan for the treatment of Alzheimer's patients within existing frameworks of care.

STUDY SUMMARY

Study Title	Feasibility study: Can reducing periodontal infection (gum disease) slow the progression of cognitive impairment associated with Alzheimer's disease
Short title	Oral Health for Brain Health
IRAS Number	315223
Sponsor ref. no.	DE/2021/7205
Study Design	An examiner blind, parallel, 2 arm randomised controlled trial in adults with early-stage-Alzheimer's Disease or Mild Cognitive Impairment (MCI), who also have periodontal disease. Participants will be randomised to an intensive or standard dental intervention.
Study Participants	Adults with early-stage-Alzheimer's Disease (AD) or Mild Cognitive Impairment (MCI), who also have periodontal disease
Planned Size of Sample (if applicable)	50
Follow up duration (if applicable)	Up to 18 months
Planned Study Period	September 2022 – May 2025
Research Question/Aim(s)	Overarching Aim:
	To show whether improved periodontal health can slow the progression of Alzheimer's Disease (AD).
	Aim of this feasibility trial:
	To assess the feasibility of conducting a Randomised Controlled Trial (RCT) of an Intensive Dental Care intervention (IDC), compared with the Standard Dental Care (SDC) provided in General Dental Practice, in AD patients to slow down decline in cognitive function
Key words	Alzheimer's Disease, cognitive decline, periodontal (gum) disease, oral health

FUNDING AND SUPPORT IN KIND

FUNDER(S)	FINANCIAL AND NON FINANCIALSUPPORT		
(Names and contact details of ALL GIVEN			
organisations providing funding and/or			
support in kind for this study)			
National institute for Health Research	Research costs: £261,791.00		
(Research for Patient Benefit): NIHR203048 NHS support and treatment costs: £11,443			

ROLE OF STUDY SPONSOR AND FUNDER

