3.1 Feasibility study objectives: show

- recruitment rates, retention rates and data completion rates
- improvement in oral health in the intervention arm patients at 12-months
- measures of cognitive decline show sensitivity to change over 12-months
- blood levels of inflammatory markers show sensitivity to changes in periodontal disease status over 12-months

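### Proof of concept for periodontal improvement and blood markers rests on the intensive-care arm alone, so it can show change but not an effect of the intervention

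*Protocol*

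**What the plan says.** Section 6.2 sets 50 participants, 25 per group, partly so that blood markers of inflammation can serve as a surrogate endpoint giving proof of concept for the underlying hypothesis. For these outcomes its only criterion is: "For the 25 in the intervention arm there is 90% power to show that periodontal improvement and blood markers of inflammation"; what must be shown is an 80% interval that excludes zero, for effects above 0.6 SD. The companion statement on cognition uses all participants: "Effect sizes for MCI/AD progression (n=50) will have 90% power to show 80% confidence intervals do not contain zero", for effects above 0.4 SD.

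The matching objective in section 3.1 is "improvement in oral health in the intervention arm patients at 12-months", with no comparison against SDC. The marker objective in the same list asks for sensitivity to changes in periodontal status and names no arm.

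Section 4.4 promises 80% intervals for all effect sizes (laboratory, periodontal, cognitive) to help plan the full trial and to illustrate sensitivity to change. It does not say whether they are within-arm or between-arm.

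Section 4.2.1 gives both arms a shared package: "All participants will receive oral and written oral hygiene education, toothpaste, a power toothbrush". Section 6.1.1 requires pockets above 4 mm with bleeding at entry. Sections 4.1 and 4.2.4 have both arms assessed periodontally and giving blood and saliva at baseline, 6 and 12 months. Section 3.2 bases progression to a full trial on recruitment and data completion.

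**The concern.** An interval for change in one arm measures everything that happened to those patients between the two visits. Here that includes the intervention, the shared toothbrush and education, and the effect of being told that they have periodontitis, which both arms are. For pocket depth and bleeding it also includes regression to the mean, because patients enter on high values of those measures. Selection is not on blood markers, so regression to the mean does not apply directly to them, but the shared package might still affect them.

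If the IDC-arm interval is read as proof of concept, improvement common to both arms counts as an IDC effect, and an inflated effect may be carried into the size of the definitive trial. The randomised control arm, which would remove this problem, is measured on the same schedule but plays no part in the criterion in section 6.2.

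**Working it through.** **Inputs.** From section 6.2: two-sided 80% interval (10% in each tail), 90% power, 25 per arm, 0.6 SD in the IDC arm and 0.4 SD for n=50. The 80% completion rate is used there only to illustrate precision; applying it to power (20 per arm) is an assumption. The protocol gives no SD of change, no expected change under SDC and no baseline correlation.

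**1. Reproducing the plan's figure as within-arm change.** Power = P(T > t(0.90, n−1)), where T is noncentral t with noncentrality d√n.
- d=0.6, n=25: noncentrality 3.00, power 95.2%.
- d=0.6, n=20: noncentrality 2.68, power 91.0%.
- By the normal approximation, n = (2 × 1.2816/0.6)² = 18.25, and 18.25/0.8 = 22.8, so 23 against the planned 25.
- Companion figure, d=0.4: 93.6% at n=50 and 88.9% at n=40.

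Both stated figures are close to one-sample calculations that allow for about 80% completion.

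**2. The same effects as a between-arm contrast.** Noncentrality d√(n/2), 2n−2 degrees of freedom, two-sided 80% interval.

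| | 25 per arm | 20 per arm |
|---|---|---|
| Power at 0.6 SD | 79.4% | 72.4% |
| Power at 0.4 SD | 54.8% | 48.8% |
| Effect with 90% power | 0.73 SD | 0.82 SD |

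By the normal approximation, 90% power at 0.6 SD needs 2 × 18.25 = 36.5, so 37 evaluable per arm (74 in total), or 37/0.8 = 46.25, so 47 per arm at 80% completion.

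One two-arm variant does reach the stated power. With one-sided alpha 0.20 and 25 per arm, Φ(0.6√12.5 − 0.842) = 90.0%. It conflicts with the wording (the intervention arm; an 80% interval excluding zero) and gives only Φ(0.4√12.5 − 0.842) = 72% for the 0.4 SD companion.

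**3. What the one-arm criterion does if IDC adds nothing.** Let both arms improve by g SDs of change. The values of g are assumptions. The probability that the IDC-only 80% interval excludes zero in the favourable direction is the step 1 formula with d = g:

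| g | 0 | 0.2 | 0.3 | 0.4 | 0.5 |
|---|---|---|---|---|---|
| n=25 | 10% | 38% | 58% | 75% | 88% |
| n=20 | 10% | 34% | 51% | 68% | 82% |

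A between-arm interval gives 10% throughout, because g cancels.

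**4. What baseline adjustment would recover.** With equal variances and baseline correlation r, the SD of change is σ√(2(1−r)) and the residual SD after adjustment is σ√(1−r²). In SD-of-change units, the step 2 detectable effect is therefore multiplied by √((1+r)/2), ignoring the few degrees of freedom spent on covariates.
- r=0.5: factor 0.866, giving 0.63 SD (25 per arm) to 0.71 SD (20 per arm).
- r=0.7: factor 0.922, giving 0.67 to 0.76 SD.

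Multiplying by √(1−r²) instead would express the effect in SDs of the 12-month score, which cannot be set against a 0.6 in SDs of change.

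**The case against.** The strongest defence is that section 4.4 presents the intervals as evidence of sensitivity to change and does not confine them to one arm. Within-arm change is a legitimate estimate for that purpose, and an analysis plan not seen here may add a between-arm estimate. This stands as far as it goes. It does not rescue section 6.2, which calls the marker result proof of concept for the hypothesis. If the intended analysis is between-arm, the stated 90% at 0.6 SD is not its power.

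The protocol also expects little improvement under SDC: section 4.2.3 argues that bleeding is unlikely to fall without tailored instruction. That may be right, so improvement in both arms is a possibility of unknown size. The control arm is there to test it.

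A reader might infer that a false proof of concept would trigger the full trial. Section 3.2 does not support that: progression depends on recruitment and data completion, and no rule declares success from this interval.

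A reader might also link the interval to the lay summary's "we would be able to strongly recommend the use of a personalised dental plan for the treatment of Alzheimer's patients". That sentence is conditional on evidence for a larger trial and on the plan helping, and is not tied to the IDC-arm interval. Its optimism is a secondary wording matter, not proof of an analysis error.

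**Conclusion.** The point holds in a limited form. The criterion in section 6.2 and the oral-health objective in section 3.1 look at the IDC arm alone, and the arithmetic confirms a one-sample calculation. Such a result can support sensitivity to change but cannot be attributed to IDC. For the contrast that could be, power at 0.6 SD is 79% with 25 per arm or 72% with 20, against the 90% stated.

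The 10% to 88% range is illustrative. It rests on assumed shared shifts of 0 to 0.5 SD and on no added IDC effect; with no shared shift there is no excess. It would go too far to say that the whole plan ignores the randomised control, since section 4.4 leaves the contrast open, or that both arms are bound to improve. The harm is to the proof-of-concept statement and the planning effect sizes. This is not a must-fix for the progression decision.

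**What to change.** 1. For each periodontal score and blood marker, make the IDC minus SDC difference at 12 months, adjusted for the baseline value and the randomisation strata actually used, with its 80% interval, the proof-of-concept and planning estimate.
2. Report within-arm change, including the oral-health objective in section 3.1, as descriptive evidence of sensitivity to change only.
3. Restate section 6.2 for the between-arm contrast: 90% power at about 0.73 SD with 25 per arm, or 0.82 SD with 20 completers per arm, before adjustment. If a gain from adjustment is claimed, state the assumed correlation and keep the same SD units.
4. As a lesser change, limit the lay dissemination text to whether a definitive trial is warranted.

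The cost is wording. The control data are already scheduled, so no new visits, samples or patients are needed. The downside is that the stated detectable effect becomes larger, and keeping 90% power at 0.6 SD without adjustment would need 74 evaluable patients.
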